### **6.3 Dose Modification and Management of Immune-Related Adverse Events, Infusion Reactions, and Cytokine Release Syndrome**

One level dose reduction per the dose escalation scheme, for toxicity is allowed. If the toxicity is equivalent to a DLT (see Section 6.1.3) then continued treatment at a lower dose level needs approval by the sponsor and/or SRC.

If immune related adverse events occur, these should be managed according to the ASCO2018 guideline for immune checkpoint inhibitors, and therapy should be continued with close monitoring for Grade 1 toxicities, with the exception of some neurologic, hematologic, and cardiac toxicities. For Grade 2 toxicities, corticosteroids may be administered, and dose should be held until resolution of the AE. Grade 3-4 toxicities treatment with PTX-35 should be discontinued and treatment with high-dose corticosteroids initiated.

All patients should be observed for infusion-related reactions (e.g., back pain, fever and/or shaking chills, flushing and/or itching, alterations in heart rate and blood pressure, dyspnea or chest discomfort, skin rashes, or anaphylaxis). For Grade 1-2 reactions, the infusion should be temporarily interrupted and then resumed when symptoms are resolved. If symptoms have not resolved in 15 minutes treatment with acetaminophen and/or antihistamines may be administered per institutional standard at the discretion of the investigator. Premedication prior to subsequent doses is allowed and should be considered. Grade 3 or 4 infusion related reactions should be managed per institutional standards (e.g., IM epinephrine, followed by IV diphenhydramine and ranitidine, and IV glucocorticoid), and treatment with PTX-35 should be permanently discontinued.

Cytokine release syndrome (CRS) is associated with elevated circulating levels of several cytokines including interleukin (IL)-6 and interferon  $\gamma$ , and uncontrolled studies demonstrate that immunosuppression using tocilizumab, an anti-IL-6 receptor antibody, with or without corticosteroids, can reverse the syndrome. However, because early and aggressive immunosuppression could limit the efficacy of the immunotherapy, current approaches seek to limit administration of immunosuppressive therapy to patients at risk for life-threatening consequences of the syndrome. The treatment algorithm suggested by Lee et al outlined in Figure 4 should be used to manage such reactions.

**Figure 4:** Current concepts in the diagnosis and management of cytokine release syndrome

## 6.4 Concomitant Treatment

Patients must not receive any other concurrent anti-cancer therapy, including investigational agents while on study treatment.

Unexpected serious adverse reactions, including for example severe allergic reactions, may be treated according to standard-of-care and institutional practice without limitations, including antihistamines, corticosteroids, cytokine antagonists, antipyretics and analgesics.

While on treatment in the study, use of the type of medications specified below should be avoided. PTX-35 will be temporarily stopped for the period of time these medications are used.

- Immunosuppressive agents (i.e., methotrexate, azathioprine, and TNF $\alpha$  blockers), except to treat a PTX-35-related adverse event
- Systemic corticosteroids > 10 mg daily prednisone equivalent

Ocular, intra-articular, intranasal, and inhalational corticosteroids are allowed.

For patients with bone metastases requiring medication for treatment and/or prevention of skeletal-related events bisphosphonates are permissible but RANK-ligand inhibitors, such as Denosumab are prohibited throughout the trial.

Supportive treatment may include anti-emetic, anti-diarrheal, anti-pyretic, anti-histamines, analgesics, antibiotics, and blood products. At the discretion of the treating physician, patients may receive anti-histamine prophylaxis according to the standard of care in clinical practice.

## 6.5 Monitoring Patient Compliance

This study will be monitored by Pelican Therapeutics or its designee according to ICH E6 guidelines of GCP. The study site monitor will regularly visit the study sites to ensure that the study is conducted according to the protocol and GCP principles.

# 7.0 STUDY EVALUATIONS

## 7.1 Schedule of Assessments

Study visit and assessment schedule are summarized in [Table 2](#) and described in Sections [7.2](#) through [7.6](#).

**Table 2: Schedule of Assessments**

Study procedures	Pre-Treatment	Study Treatment										Follow-Up		
		Cycle 1					Cycle 2					Cycle ≥3 D1	30-Day Safety Follow-Up	Post-Treatment Follow-Up (q8 wks)
		D1	D2	D4	D7	D10	D1	D2	D4	D7	D10			
Informed consent	x a													
Medical history	x a													
Physical exam	x a	x c					x					x		
Weight	x a	x c					x					x		
Vital signs	x a	x d					x d					x d	x	
ECOG performance status	x b	x c					x					x	x	
ECG e	x a	x c					x					x		
Tumor measurement f	x a	Every 8 weeks (± 1 week) from C1D1 until PD or change in cancer treatment										N/A		
Hematology g	x b	x c					x					x	x	
Serum chemistry h	x b	x c					x					x	x	
Pregnancy test i	x b													
Confirmation of eligibility	x	x												
PTX-35 administration j		x					x					x		
TENIVAC administration		x												
Blood sample for HLA k	x													
Blood sample for PK l		x	x	x	x	x	x	x	x	x	x	x l		
Blood sample for cytokines		x m					x m					x m		
Blood sample for ATA and anti-TENIVAC titer n		x					x					x	x	
Blood sample for immunological effect o		x			x		x			x			x	
Prior/concomitant medications review	x a	x	x	x	x	x	x	x	x	x	x	x	x p	x p
Adverse Event assessment		x	x	x	x	x	x	x	x	x	x	x	x q	x q
Survival Status														x r

### **Footnotes to Schedule of Assessments**

- a. Within 28 days prior to study treatment initiation.
- b. Within 7 days prior to study treatment initiation.
- c. If performed within 3 days of Cycle 1 Day 1, these tests do not need to be repeated unless clinically indicated.
- d. Vital signs, including blood pressure, heart rate, respiration rate, and temperature. During Cycle 1 and 2: prior to PTX-35 administration and at 30 min ( $\pm 5$  min) and 1h ( $\pm 5$  min) after end of PTX-35 infusion. Other cycles: only prior to PTX-35 administration.
- e. 12-lead ECGs (in triplicate) to be performed with patient in a semi-recumbent position at screening and on Day 1 of each cycle prior to PTX-35 administration.
- f. Tumor measurement per RECIST 1.1. Baseline tumor assessment should be performed within 28 days prior to study treatment initiation. Patients will be evaluated every 8 weeks ( $\pm 1$  week) from C1D1 until disease progression, regardless of dose delays.
- g. Hematology, including hemoglobin, WBC with differential, and platelet count (Approximately 5 mL blood per draw).
- h. Serum chemistry including: sodium, potassium, chloride,  $\text{CO}_2$ , BUN, creatinine, glucose, calcium, albumin, total protein, total bilirubin, AST, ALT, alkaline phosphatase, TSH (Approximately 5 mL blood per draw).
- i. For women of childbearing potential only, a negative serum or urine  $\beta$ -hCG must be documented within 7 days prior to first dose of PTX-35.
- j. PTX-35 is administered as an IV infusion. Each patient must remain in clinic for a 6-hour safety observation period after the end of the PTX-35 infusion unless the SRC reduces the required observation period.
- k. HLA sample will be collected pre-dose at Cycle 1 only.
- l. PK samples will be collected at the following timepoints: pre-dose; 30min ( $\pm 5$ min), 2hr ( $\pm 5$ min), 4hr ( $\pm 5$ min), 24hr ( $\pm 2$ hr), 72hr ( $\pm 2$ hr), 144hr ( $\pm 2$ hr), 216hr ( $\pm 2$ hr) after end of PTX-35 infusion for Cycles 1 and 2, and pre-dose at Cycle 3 only.
- m. Cytokine blood sample collection at the following timepoints during Cycle 1 and 2: prior to PTX-35 administration and at 2 hr ( $\pm 5$ min) after end of PTX-35 infusion. Collection at cycle 3 and beyond is only required if the patient is symptomatic (i.e., flu-like or allergic reactions) prior to PTX-35 infusion and at 2 hr ( $\pm 5$ min) after end of PTX-35 infusion.
- n. Pre-dose blood sample collection to monitor development of anti-therapeutic antibodies (ATA) and anti-TENIVAC antibody titer.
- o. Blood sample collection for immunological effect; Day 1 (prior to PTX-35 administration) and Day 7 for Cycle 1 and Cycle 2, and 30-Day Safety Follow-Up only.
- p. In post-treatment and survival follow-up, concomitant medications limited to subsequent anti-cancer therapy.
- q. If  $> 30$  days since last dose, only record AEs if deemed related to Investigational Product
- r. Survival status and subsequent anti-cancer therapy information will be collected approximately every 12 weeks in a clinic visit or by telephone/electronic communication, from the time of disease progression or initiation of new anti-cancer treatment until death.

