#### **4.5 Duration of Therapy**

Upon completion of the first two treatment cycles (i.e., 4 weeks, with at least 2 doses of PTX-35), in the absence of disease progression and unacceptable toxicity, patients may continue to be treated with PTX-35 at the same dose and schedule until disease progression, death, patient's withdrawal of consent, Investigator's decision to remove patient, or intolerable toxicity, whichever occurs first.

At the discretion of the Investigator, and in the absence of clinical deterioration, treatment with PTX-35 may continue beyond initial evidence of radiological progression as per Section 8.2.1.

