## 5.0 SELECTION AND WITHDRAWAL OF PATIENTS

### 5.1 Inclusion Criteria

Patients **must** meet all of the following inclusion criteria before they will be allowed to participate in the trial:

1. Be willing and have the capacity to sign the written informed consent form.
2. Be male or female of at least 18 years of age at the time of signing informed consent.
3. Have a documented diagnosis of metastatic or advanced, unresectable solid tumor disease. Patient must have progressed or recurred following standard of care (SOC) therapies, or are ineligible for, or who refuse, other safe and effective SOC therapies, and whom the Investigator believes may benefit from experimental treatment with PTX-35.

4. Have an acceptable organ function, as defined below:
  - a. Albumin  $\geq$  2.5 g/dL
  - b. Total bilirubin  $< 3.0 \times$  upper limit of normal (ULN) unless patient has Gilbert's syndrome.
  - c. Alanine transaminase (ALT) and aspartate transaminase (AST)  $\leq 3.0 \times$  ULN, or  $\leq 5 \times$  ULN in the case of liver metastases.
  - d. Calculated or measured creatinine clearance  $> 35$  mL/minute per the Cockcroft-Gault formula.
  - e. Absolute neutrophil count  $\geq 1,500/\text{mm}^3$
  - f. Hemoglobin  $\geq 9$  g/dL.
  - g. Platelet count  $\geq 100,000/\text{mm}^3$
5. Have an Eastern Cooperative Oncology Group (ECOG) performance status of 0 to 2 ([APPENDIX I](#)).
6. Have life expectancy of at least three months.
7. Patients, both females and males, of childbearing/reproductive potential must agree to use adequate contraception, or continuous abstinence, while included in the trial and for six months after the last treatment with PTX-35.

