### **5.4 Withdrawal Criteria**

Protocol therapy will be discontinued at any time if any of the following situations occur:

1. Progressive disease (not including unconfirmed radiographic PD if Investigator opts to continue treatment as outlined in section [8.2.1](#)).
2. Adverse event.
  - The development of toxicity which, in the Investigator's judgment, precludes further therapy.
  - Unacceptable adverse event(s).
  - Intercurrent illness that prevents further administration of treatment.
3. Withdrawal by subject.
4. Lost to follow-up.
5. Non-compliance.
6. At the discretion of the Investigator/physician decision.

7. Death.
8. Pregnancy.
9. Study termination.

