## 7.2 Pre-treatment

Within 28 days from C1D1:

- Sign written informed consent
- Medical history including prior cancer treatments, prior surgeries (requiring an overnight hospitalization), and pre-existing clinical signs and symptoms
- Record prior medications (taken within 30 days of C1D1)
- Complete physical exam
- Weight
- Vital signs (blood pressure, heart rate, respiratory rate, and temperature)
- ECG (a standard 12-lead ECG in triplicate, approximately 2 to 5 minutes apart) is taken while patient is in a semi-recumbent position
- Imaging for tumor measurements by RECIST 1.1 ([APPENDIX II](#))
- Confirmation of eligibility

Within 7 days from C1D1:

- ECOG performance status ([APPENDIX I](#))
- Blood draw for hematology
- Blood draw for serum chemistry
- Pregnancy test for women of childbearing potential

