#### 8.1.2 Reporting of Adverse Events

##### 8.1.2.1 Adverse Events

An adverse event (AE) is any untoward medical occurrence in a patient or clinical investigation subject administered a pharmaceutical product that does not necessarily have a causal relationship with the treatment. An adverse event can be any unfavorable and unintended sign (including a laboratory finding), symptom or disease temporally associated with the use of an Investigational Product, whether or not related to the Investigational Product.

The AE reporting period starts on Cycle 1 Day 1 after the first dose of PTX-35. If an AE occurs before the first dose of study drug it will be captured as baseline and considered part of medical history unless it directly related to a study procedure (in which case it may be reported as an AE). At each evaluation, patients should be interviewed in a non-directed manner to elicit potential adverse reactions from the patient. The occurrence of an adverse event will be based on changes in the patient's physical examination, laboratory results, and/or signs and symptoms.

All adverse events (except Grade 1 and 2 laboratory abnormalities that do not require an intervention), regardless of causal relationship, are to be recorded in the case report form and source documentation. The Investigator must determine the intensity of any adverse events according to the NCI Common Terminology Criteria for Adverse Events (CTCAE) version 5.0 and their causal relationship. Those AEs not covered by these criteria will be graded as follows:

1. Mild: Discomfort noticed, but no disruption of normal daily activity. Prescription drug not ordinarily needed for relief of symptom but may be given because of personality of patient.
2. Moderate: Discomfort sufficient to reduce or affect normal daily activity. Patient is able to continue in study; treatment for symptom may be needed.
3. Severe: Incapacitating, severe discomfort with inability to work or to perform normal daily activity. Severity may cause cessation of treatment with test drug; treatment for symptom may be given and/or patient hospitalized.
4. Life-Threatening: Symptom(s) place the patient at immediate risk of death from the reaction as it occurred; it does not include a reaction that, had it occurred in a more serious form, might have caused death.
5. Fatal: Event caused the death of the patient.

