### **8.1.2.5 Pregnancy**

Any pregnancy detected during the study, or that occurs within 30 days after stopping study medication, must be reported immediately to the Investigator. Pregnancy, in and of itself, is not regarded as an adverse event, unless there is suspicion that study medication may have interfered with the effectiveness of a contraceptive medication. If the patient becomes pregnant while on-study, the study drug should be immediately discontinued. Pregnancy information about a female patient or a female partner of a male patient should be reported immediately from the time the Investigator first becomes aware of a pregnancy or its outcome. This will be performed by the Investigator per instructions from the Sponsor or its designee.

Any pregnancy complication, spontaneous abortion, elective termination of a pregnancy for medical reasons, outcome of stillbirth, congenital anomaly/birth defect, or serious adverse event in the mother will be recorded as an SAE and will be reported as described in Section [8.1.2.6](#).

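### Pregnancy is tested once, before the first dose, yet PTX-35 repeats every 14 days without a fixed end and must stop for pregnancy

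*Combined protocol and SAP*

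**What the plan says.** **Testing.** Table 2 marks the pregnancy test in the Pre-Treatment column only. Footnote i states that a negative serum or urine beta-hCG "must be documented within 7 days prior to first dose of PTX-35". Section 7.2 lists "Pregnancy test for women of childbearing potential" among the assessments due within 7 days of Cycle 1 Day 1 (C1D1). The visit lists in Sections 7.3.1 to 7.3.4, 7.4, 7.5 and 7.6 contain no pregnancy test, and neither do the hematology and chemistry panels in footnotes g and h.

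**Dosing.** PTX-35 is given on Day 1 of each 14-day cycle. After two cycles, Section 4.5 provides that "patients may continue to be treated with PTX-35 at the same dose and schedule until disease progression" or another listed event. It sets no maximum number of cycles.

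**Stopping.** Section 5.4 introduces its list with "Protocol therapy will be discontinued at any time if any of the following situations occur"; item 8 is pregnancy. Section 8.1.2.5 adds: "If the patient becomes pregnant while on-study, the study drug should be immediately discontinued".

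**Other safeguards.** Under inclusion criterion 7 in Section 5.1, patients of reproductive potential "must agree to use adequate contraception, or continuous abstinence, while included in the trial" and for six months after the last dose.

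**The concern.** The protocol treats exposure during pregnancy as something to prevent. It excludes pregnant women, asks for a laboratory test rather than the patient's word before dose 1, and ends treatment if pregnancy occurs. From dose 2 onward the test disappears while the stop rule stays.

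Contraception lowers the chance of pregnancy but does not detect a failure. The remaining assessments have other purposes. At each evaluation, under Section 8.1.2.1, "patients should be interviewed in a non-directed manner to elicit potential adverse reactions from the patient", and Section 8.1.2.5 says "Pregnancy, in and of itself, is not regarded as an adverse event", except where the drug is suspected of having impaired a contraceptive. A site that follows the schedule to the letter could therefore keep dosing through an unrecognised pregnancy.

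This is a first-in-human trial, and Section 2.6 states that there are no human safety data for PTX-35. What is at stake is the safety of a subset of patients, not the validity of any analysis.

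**Working it through.** The plan gives no figure to reproduce. The check is a reading of the schedule visit by visit, followed by calendar arithmetic.

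**Inputs**

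- Test window: 0 to 7 days before C1D1 (Table 2 footnote i, Section 7.2).
- Cycle length: 14 days, dose on Day 1 (Section 4.2).
- Visit window: +2 days for Cycle 2 Day 1 and later (Sections 7.3.3 and 7.3.4).
- Scans: every 8 weeks ± 1 week from C1D1 (Table 2 footnote f).

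**Step 1: scheduled pregnancy tests by visit**

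| Visit | Section | Pregnancy test |
|---|---|---|
| Pre-treatment | 7.2 | 1 |
| C1D1 | 7.3.1 | none (eligibility re-verified, no new test named) |
| Days 2, 4, 7, 10 of Cycles 1 and 2 | 7.3.2 | none |
| C2D1 | 7.3.3 | none |
| Day 1 of Cycle 3 and beyond | 7.3.4 | none |
| 30-day visit, post-treatment and survival follow-up | 7.4 to 7.6 | none |

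The total is one test before the first dose and none after it. Footnote i and the visit lists agree with the table, so damage to the table in text extraction does not explain the result.

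**Step 2: age of the single test at later doses**

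Age at dose k = days from C1D1 to dose k + test age at C1D1.

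- C2D1: (14 to 16) + (0 to 7) = 14 to 23 days.
- C5D1, no delays and no use of the visit window: 4 × 14 + (0 to 7) = 56 to 63 days.
- C5D1, if the 2-day window is used in full at each of the four visits and the shifts accumulate: up to 56 + 4 × 2 + 7 = 71 days.

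Treatment has no fixed end, so the age has no upper bound.

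**Step 3: doses given on the strength of that test**

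With no delays, dose k falls on day 1 + 14(k − 1).

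- By the first on-treatment scan: doses at weeks 0, 2, 4 and 6 = 4, or 5 if the scan follows the week-8 dose within the window to week 9.
- By 24 weeks: the twelfth dose falls on day 1 + 14 × 11 = 155, so 12 doses precede day 169.

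**Step 4: the same quantities with added testing**

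- Test on Day 1 of each cycle from Cycle 2: every later dose has a same-day result.
- Test at Cycles 3, 5, 7 and so on: 28 / 14 = 2 doses per result. The pre-treatment test likewise covers only Cycles 1 and 2.

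**The case against.** The strongest reply is that nothing here is contradictory. Sections 5.4 and 8.1.2.5 say what to do once a pregnancy is known; neither promises periodic testing. There are real safeguards: contraception or abstinence throughout, a physical examination on Day 1 of each cycle, adverse event review at every visit of Cycles 1 and 2 and on Day 1 of each later cycle, and a duty to report any pregnancy at once. The adverse event definition is broad enough to capture symptoms of early pregnancy, and an investigator may test at any time. The consent pages and the Investigator's Brochure are not available here and may tell patients to report a suspected pregnancy. The documents at hand describe no embryo-fetal hazard, and the affected group may be very small.

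Most of this is accurate, and it makes the gap smaller. It does not close it. Each safeguard prevents pregnancy, depends on the patient or the investigator suspecting one, or finds it by chance. The wording in Section 8.1.2.5 is advisory, but Section 5.4 is mandatory, so the stop rule stands either way.

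One cost raised on this side deserves weight. C2D1 lies in the DLT window. A positive result there holds the second dose, and Section 6.1.2 makes the cohort decision wait for all second doses. Under Section 5.4.2, a patient who misses the second dose for a non-toxicity reason is replaced. If pregnancy is confirmed, the existing rule would impose the same consequence. A false positive could cause a short delay. This should be rare, and testing from Cycle 3 avoids it.

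**Conclusion.** The concern holds. There is one scheduled test before the first dose and none afterwards, while dosing is open-ended and pregnancy requires treatment to stop. The test is 14 to 23 days old at the second dose and, with no delays, 56 to 63 days old at the fifth.

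These figures describe the schedule, not harm. They assume that doses are given on the planned calendar apart from the stated window; permitted holds would make the test older still. No number of avoided doses is claimed, because the count of women of childbearing potential is not given and neither is any pregnancy rate. There is no effect on endpoints, the DLT rule, escalation or sample size. This is a worthwhile, low-cost improvement in safety monitoring that lets an existing stop rule work.

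**What to change.** For women of childbearing potential, require a negative urine or serum beta-hCG on Day 1 of each cycle from Cycle 2, with the result read before the infusion. The minimum is every second cycle (Cycles 3, 5, 7 and so on, about every 4 weeks), which also keeps the test out of the DLT window. Make the change in:

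- Table 2, the Cycle 2 D1 and Cycle ≥3 D1 columns, and footnote i;
- Sections 7.3.3 and 7.3.4, one bullet each.

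State that a positive result holds that dose until it is confirmed. Section 5.4 item 8 and Section 8.1.2.5 then apply unchanged. A test at the 30-day visit is optional; it would support only the 30-day pregnancy reporting rule, not the treatment stop.

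**Cost.** One schedule line with its footnote, and two bullets. No new visit is needed. A urine test needs no blood; serum can come from the Day 1 chemistry draw if the result is back before infusion. The burden is a small test cost and a short wait in a subset of patients, plus, if testing starts at Cycle 2, the rare held second dose described above.
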